### 8.8.5 Evidence synthesis

Results from analyses described in section 8.8 Data analysis will be presented separately for each database and no meta-analysis of results will be conducted.

## 9. DATA MANAGEMENT

### 9.1 Data management

All databases are mapped to the OMOP common data model. This enables the use of standardised analytics and tools across the network since the structure of the data and the terminology system is harmonised. The OMOP CDM is developed and maintained by the Observational Health Data Sciences and Informatics (OHDSI) initiative and is described in detail on the wiki page of the CDM: <https://ohdsi.github.io/CommonDataModel> and in The Book of OHDSI: <http://book.ohdsi.org>

The analytic code for this study will be written in R. Each data partner will execute the study code against their database containing patient-level data and will then return the results set which will only contain aggregated data. The results from each of the contributing data sites will then be combined in tables and figures for the study report.

### 9.2 Data storage and protection

For this study, participants from various EU member states will process personal data from patients which is collected in national/regional electronic health record databases. Due to the sensitive nature of this personal medical data, it is important to be fully aware of ethical and regulatory aspects and to strive to take all reasonable measures to ensure compliance with ethical and regulatory issues on privacy.

All databases used in this study are already used for pharmaco-epidemiological research and have a well-developed mechanism to ensure that European and local regulations dealing with ethical use of the data and adequate privacy control are adhered to. In agreement with these regulations, rather than combining person level data and performing only a central analysis, local analyses will be run, which generate non-identifiable aggregate summary results.

The output files are stored in the DARWIN Digital Research Environment. These output files do not contain any data that allow identification of subjects included in the study. The DRE implements further security measures in order to ensure a high level of stored data protection to comply with the local implementation of the General Data Protection Regulation (GDPR) (EU) 679/2016 in the various member states.

## 10. QUALITY CONTROL

### General database quality control

A number of open-source quality control mechanisms for the OMOP CDM have been developed (see Chapter 15 of The Book of OHDSI <http://book.ohdsi.org/DataQuality.html>). In particular, it is expected that data partners will have run the OHDSI Data Quality Dashboard tool (<https://github.com/OHDSI/DataQualityDashboard>). This tool provides numerous checks relating to the conformance, completeness and plausibility of the mapped data. Conformance focuses on checks that describe the compliance of the representation of data against internal or external formatting, relational, or

	D2.2.3 –Study Protocol for P2 C1-008	
	Author(s): [name], [name]	Version: v3.1 – Final
		Dissemination level: public

computational definitions, completeness in the sense of data quality is solely focused on quantifying missingness, or the absence of data, while plausibility seeks to determine the believability or truthfulness of data values. Each of these categories has one or more subcategories and are evaluated in two contexts: validation and verification. Validation relates to how well data align with external benchmarks with expectations derived from known true standards, while verification relates to how well data conform to local knowledge, metadata descriptions, and system assumptions.

#### Study specific quality control

When defining cohorts for drugs, a systematic search of possible codes for inclusion will be identified using CodelistGenerator R package (<https://github.com/darwin-eu/CodelistGenerator>). A pharmacist will review the codes of the opioids of interest. This software allows the user to define a search strategy and using this will then query the vocabulary tables of the OMOP common data model so as to find potentially relevant codes. In addition, DrugExposureDiagnostics (26) will be run if needed to assess the use of different codes across the databases contributing to the study.

The study code will be based on two R packages currently being developed to (1) estimate treatment patterns (initiation, switching or discontinuation) and (2) characterize drug utilization (duration of use) using the OMOP common data model. These packages will include numerous automated unit tests to ensure the validity of the codes, alongside software peer review and user testing. The R package will be made publicly available via GitHub.

## **11. LIMITATION OF THE RESERACH METHODS**

The study will be informed by routinely collected health care data and so data quality issues must be considered, despite the data quality checks. One crucial aspect pertains to the identification of patients with MDD. It is worth noting that the accuracy of these records may vary across different databases. While a relatively low rate of false positives is expected (i.e., cases recorded with a condition they do not truly have), the likelihood of false negatives (i.e., cases with the condition not being recorded) may be higher, particularly in databases lacking patient-level linkage between primary care and secondary care data. In this study, the MDD phenotype will be defined solely based on physician-diagnosed cases identified using relevant SNOMED codes, rather than relying on standardized depression rating scales or individual clinical interviews, often regarded as the "gold standard" for MDD diagnosis. It is important to note that previous studies in CPRD GOLD, IQVIA DA Germany, and SIDIAP have more likely included well-phenotyped MDD cases.

Furthermore, the documentation of medication use and co-morbidities, necessary for patient -level characterization, may vary across databases. In databases where information on MDD treatment is available, the recording of medication use may be incomplete, especially in primary care databases like CPRD GOLD that lack linkage to hospital data. Additionally, it is essential to highlight that the mere recording of a prescription or dispensing does not necessarily imply that the patient used the prescribed medication. Furthermore, assumptions around the duration of drug use will be unavoidable such as using prescribed duration which may not accurately reflect the actual duration of drug exposure. For databases, where duration cannot be calculated due to e.g. missing information on quantity or dosing, treatment duration will not be provided.

	D2.2.3 –Study Protocol for P2 C1-008	
	Author(s): [name], [name]	Version: v3.1 – Final
		Dissemination level: public

For the treatment pattern analysis, we will look at specific time intervals following treatment initiation namely at week 4, 6, 8, 12 and 24 following treatment initiation. Only patients with sufficient follow-up at these intervals will be included for this analysis, implying that patients for instance which were initially included for the analysis at week 4 might not longer be included at week 6 because of lost to follow-up. As part of the results, we will provide the number of individuals included in the analysis at the different time intervals which will provide information on the extent of people who dropped out from the analysis. If the percentage of people who dropped from the analysis at week 24 is high (where high is defined as more than 50% of individuals participating at week 4 do not longer participate at week 24), we will do a sensitivity analysis where i) we assume that the people who were lost for follow-up continued treatment and ii) we assume that the people who were lost to follow-up discontinued treatment. As this analysis can not be generated by the treatment pattern package, we will only do this for the overall analysis (thus not stratified by age and sex).

The number of pills (per package) of the antidepressant of interest might vary by countries which might bias the proportion of individuals continuing treatment. Indeed, if the antidepressant is dosed as one pill daily, and the initial prescription is a package of 30 pills, by definition the patient will be considered as having continued treatment at week 4 even if the patient discontinued treatment in the meantime. To contextualize this potential misclassification, we will provide information on the median quantity (with min, max, P25 and P75) by type of antidepressant and by database.

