#### Patient-level characterisation: Duration of antidepressant use

The calculation of individual prescription/dispensing durations (in days) will be derived from the DRUG\_EXPOSURE table within the CDM. This table contains the drug\_exposure\_start\_date and the drug\_exposure\_end\_date, which are populated during the Extraction Transform and Load (ETL) process based on available source data. The advantage of this approach is that the drug exposure duration is directly obtained, eliminating the need to infer it from other information during analysis. This ensures a consistent analytical pipeline across all databases. New users will be selected based on their first prescription of the respective antidepressant class of interest after the start of the study. For each patient, at least 1 year of data visibility will be required prior to that prescription. New users will be required to not have been exposed to the drug of interest for at least 1 year prior the current prescription. If the start date of a prescription does not fulfil the exposure washout criteria of 1 year of no use, the whole exposure is eliminated.

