#### Drug exposure calculations

Drug eras will be defined as follows: Exposure starts at date of the first prescription after the first MDD diagnosis. For each prescription, the estimated duration of use is retrieved from the drug exposure table in the CDM. Subsequent prescriptions for the same drug will be combined into continuous exposed episodes (drug eras) using the following specifications:

Two drug eras will be merged into one continuous drug era if the distance in days between end of the first era and start of the second era is  $\leq 7$  days. The time between the two joined eras will be considered as exposed to the first era as show in in Figure 1.

	D2.2.3 –Study Protocol for P2 C1-008	
	Author(s): [name], [name]	Version: v3.1 – Final
	Dissemination level: public	

[figure not shown]

Gap era joint mode	Schematics	Dose in between	Cumulative dose	Cumulative time
“first”		$d_1$	$d_1 \cdot (x_1 + x_{12}) + d_2 \cdot x_2$	$x_1 + x_{12} + x_2$
“second”		$d_2$	$d_1 \cdot x_1 + d_2 \cdot (x_2 + x_{12})$	$x_1 + x_{12} + x_2$
“zero”		0	$d_1 \cdot x_1 + d_2 \cdot x_2$	$x_1 + x_{12} + x_2$
“join”		NA	$d_1 \cdot x_1 + d_2 \cdot x_2$	$x_1 + x_2$

[figure not shown]

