**Figure 3. Parameters in TreatmentPatterns package (25)**

The following parameters will be defined in this study.

Parameters	Values (days)	Description
periodPriorToIndex	0	Number of days prior to the index date of the target cohort
minEraDuration	0	Minimum time an event era should last to be included in analysis
eraCollapseSize	7	Window of time between which two eras of the same event cohort are collapsed into one era
combinationWindow	7	Window of time two event cohorts need to overlap to be considered a combination treatment
minPostCombinationDuration	7	Minimum time an event era before or after a generated combination treatment should last to be included in analysis
filterTreatments	All	Select all treatments including first time occurrences and sequential repeated treatments
maxPathLength	5	Maximum number of steps included in treatment pathway

For all continuous variables, summary descriptive statistics will be reported: median and interquartile interval will be reported. For all categorical analyses, counts and percentages will be reported. A minimum cell count of 5 will be used when reporting results, with any smaller counts reported as “<5”. All analyses will be

	D2.2.3 –Study Protocol for P2 C1-008	
	Author(s): [name], [name]	Version: v3.1 – Final
		Dissemination level: public

reported by country/database, overall and stratified by age and sex when possible (minimum cell count reached).

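### Databases that cannot supply treatment duration would still report discontinuation and the switch-versus-combination split, which rest on the same end dates

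*Protocol*

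**What the plan says.** Section 11 sets a data-adequacy rule for one output: "For databases, where duration cannot be calculated due to e.g. missing information on quantity or dosing, treatment duration will not be provided". It names nothing else to be withheld.

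Section 8.8.3 gives the source of exposure time. Start and end dates come from the CDM drug exposure table, "which are populated during the Extraction Transform and Load (ETL) process based on available source data". Under Drug exposure calculations, "For each prescription, the estimated duration of use is retrieved from the drug exposure table in the CDM", and eras no more than 7 days apart are merged.

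The treatment-pathway parameters in the same section also act on eras:

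- eraCollapseSize, 7 days: "Window of time between which two eras of the same event cohort are collapsed into one era".
- combinationWindow, 7 days: "Window of time two event cohorts need to overlap to be considered a combination treatment".
- minEraDuration, 0 days: "Minimum time an event era should last to be included in analysis".

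Table 9 marks initiation, switching and discontinuation as primary outcomes. Section 8.8.3 reports all analyses by country and database, and the only limit it sets is the minimum cell count for strata. Section 8.8.5 presents each database separately.

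**The concern.** Section 11 accepts that some databases may not allow duration to be calculated and withholds the duration summary there. Discontinuation at a given week is the statement that an era ended before that week, so it needs the same end date. The overlap that separates a combination from a switch needs it too. A database judged unfit for duration is unfit for these results for the same reason, yet the plan would still report them without qualification.

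The study is meant to show whether intercurrent events occur in practice at rates similar to those in trials. A discontinuation percentage driven by how end dates were filled, rather than by when patients stopped, would distort that comparison. Nothing in the planned output would warn the reader.

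**Working it through.** No sample size, power or error rate is involved. The check has two parts.

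**1. What each output needs**

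- Initiation: start date only. Unaffected.
- Start of a new class after the first: start date only. Unaffected.
- Switch or combination: overlap of two eras, so the end date of the earlier one.
- Discontinuation: era end date.
- Duration: era end date. This is the only output that section 11 withholds.

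**2. How far the recorded duration alone can move the result**

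Inputs from the protocol: merge if the gap is at most 7 days; timepoints at 4, 6, 8, 12 and 24 weeks, that is days 28, 42, 56, 84 and 168. Assumed inputs: the refill interval *r*, the recorded duration *d*, and a patient who refills on schedule throughout. Assumed classification: discontinued by week *w* if the first era ends before day 7*w*. The protocol leaves the exact criterion to the package options.

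The protocol's own example comes first. In section 11, a pack of 30 pills taken once daily makes the patient count as continuing at week 4. By the rule, the era ends on day 30, and 30 ≥ 28, so the example is reproduced.

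In general, the gap between consecutive prescriptions is *r* − *d*. They merge if *r* − *d* ≤ 7, that is if *d* ≥ *r* − 7. Otherwise the first era ends on day *d*.

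For *r* = 30 (prescriptions on days 0, 30, …, 180):

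- *d* = 22: gap 8 > 7, era ends on day 22 < 28. Discontinued at all five timepoints.
- *d* = 23: gap 7, merged, era ends on day 180 + 23 = 203 > 168. Continuing at all five.
- *d* = 30: gap 0, era ends on day 210. Continuing at all five.

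For *r* = 90 (days 0, 90, 180):

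- *d* = 30: gap 60, era ends on day 30. Continuing at week 4 (30 ≥ 28), discontinued from week 6 (30 < 42).
- *d* = 90: gap 0, era ends on day 180 + 90 = 270. Continuing at all five.

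The prescription dates are identical within each set; only the recorded duration differs. The cut-off at 22 and 23 days may shift by one day with the day-counting convention.

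**Safeguards that might close the gap**

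- Section 11 concedes that pack quantity can misclassify continuation and offers the quantity distribution as context. Where quantity is the missing item, that table cannot be filled.
- Section 8.8.4 varies the assumption about patients lost to follow-up. It does not vary end dates.
- minEraDuration is 0, so implausibly short eras are not screened out.
- In section 10, the drug-exposure diagnostics "will be run if needed to assess the use of different codes across the databases". That is optional, and its stated aim concerns codes, not end dates.

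**The case against.** The strongest reply is that the protocol never says it will report discontinuation for a database without usable duration. Section 11 is a single contingency sentence, section 8.2 says the selected databases meet the requirements for both analyses, and an analysis plan not seen here might settle the matter. It is true that the reporting is inferred, and that no database is shown to be affected. But the protocol itself sets the adequacy rule, limits it to one output, and plans the others for every database. As written, the plan leads to publication.

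Several stronger readings are tempting, and the documents do not support them:

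- **A known default.** A reader might infer that missing end dates are set to the start date or to a fixed 30 days, and derive a range of bias from an assumed share of such records. The protocol states no filling rule. Section 11 also speaks of whole databases, not shares of records.
- **A contradiction.** Section 8.8.3 says "the drug exposure duration is directly obtained, eliminating the need to infer it", while section 11 calls duration assumptions unavoidable. Read in full, the first sentence means that duration is read from the CDM instead of being derived at analysis. The second concerns prescribed against actual use. The two are compatible.
- **A particular unfit database.** The data-source descriptions mention quantity or dosing for CPRD GOLD and IPCI only. Silence in a short description does not show that the information is missing elsewhere.
- **All switching results invalid.** The start of a new class is known without the earlier end date, so switching depends on end dates less than discontinuation does.

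**Conclusion.** The concern holds as a conditional gap. If a database cannot supply duration for the reason in section 11, the plan has no rule that stops or qualifies its discontinuation results or its split between switch and combination, and none of the existing safeguards covers the case. Initiation is not affected.

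The size of any bias cannot be given, because neither the affected databases nor the way end dates are filled is stated. What can be shown is that, for one persistent patient with assumed 30-day refills, the classification at all five timepoints turns on whether 22 or 23 days are recorded. That demonstrates sensitivity to the input and is not an estimate of error in any database. It rests on the assumed refill pattern and on taking the end of the first era as discontinuation.

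**What to change.** Extend the section 11 rule. A database that does not provide treatment duration for this reason also does not provide discontinuation or the switch-versus-combination split. Alternatively, it provides them only flagged, with the end-date imputation rule stated and a sensitivity analysis on the assumed duration. Initiation, and the start of a new class, can still be reported. Repeat the rule or cross-refer to it in section 8.8.3, so that it governs the pathway analysis.

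The text change is short. The first option costs one or more databases some outputs. The second costs a caveat, a documented imputation rule and a further analysis for those databases. The documents give no basis for a numerical pass mark or for suppressing all switching output, and do not show that the named diagnostics can tell calculated from imputed end dates, so the fix does not rely on any of these.

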## 12. MANAGEMENT AND REPORTING OF ADVERSE EVENTS/ADVERSE REACTIONS

Adverse events/adverse reactions will not be collected or analyzed as part of this evaluation. The nature of this non-interventional evaluation, through the use of secondary data, does not fulfill the criteria for reporting adverse events, according to module VI, VI.C.1.2.1.2 of the Good Pharmacovigilance Practices

## 13. GOVERNANCE BOARD ASPECTS

All data sources require approval from their respective IRB board, with the exception of IQVIA DA Germany which will not require any further specific approvals to undertake this study.

## 14. PLANS FOR DISSEMINATING AND COMMUNICATING STUDY RESULTS

### 14.1 Study Report

A PDF report including an executive summary, and the specified tables and/or figures will be submitted to EMA by the DARWIN EU® CC upon completion of the study.

An interactive dashboard incorporating all the results (tables and figures) will be provided alongside the pdf report. The full set of underlying aggregated data used in the dashboard will also be made available if requested.

## 15. OTHER RESULTS

	D2.2.3 –Study Protocol for P2 C1-008	
	Author(s): [name], [name]	Version: v3.1 – Final
		Dissemination level: public

n/a

	D2.2.3 –Study Protocol for P2 C1-008	
	Author(s): [name], [name]	Version: v3.1 – Final
	Dissemination level: public	

## 17. ANNEXES

**Appendix I:** List with preliminary concept definitions (exposure)

**Appendix II:** List with preliminary concept definitions for major depressive disorder

**Appendix III:** ENCePP checklist for study protocols

	D2.2.3 –Study Protocol for P2 C1-008	
	Author(s): [name], [name]	Version: v3.1 – Final
		Dissemination level: public

## APPENDIX I – LIST WITH PRELIMINARY CONCEPT DEFINITIONS FOR EXPOSURE

Prescriptions will be identified based on the relevant ingredient. Non-systemic products will be excluded from the code list.

CONCEPT ID	Name	ATC code
21604687	Non-selective monoamine reuptake inhibitors (NSRIs)	N06AA
21604709	Selective serotonin reuptake inhibitors (SSRIs)	N06AB
21604729	Other antidepressants (excluding N06AX25 and N06AX27)	N06AX
21604489	Psycholeptics	N05
21604490	Antipsychotics	N05A
21604564	Anxiolytics	N05B
21604606	Hypnotics and sedatives	N05C

	D2.2.3 –Study Protocol for P2 C1-008	
	Author(s): [name], [name]	Version: v3.1 – Final
		Dissemination level: public

## APPENDIX II – LIST WITH PRELIMINARY CONCEPT DEFINITIONS FOR MAJOR DEPRESSIVE DISORDER

Preliminary list – list to be reviewed prior to parametrisation of study code (using phenotype deck)

### Major Depressive Disorder

concept_id	concept_name
4152280	Major depressive disorder
4094358	Chronic recurrent major depressive disorder
45757195	Major depressive disorder in mother complicating childbirth
45757196	Major depressive disorder in mother complicating pregnancy
4304140	Recurrent major depressive disorder with atypical features
4220023	Recurrent major depressive disorder with catatonic features
4205471	Recurrent major depressive disorder with melancholic features
4324959	Recurrent major depressive disorder with postpartum onset
4031328	Chronic major depressive disorder, single episode
35615151	Recurrent mild major depressive disorder co-occurrent with anxiety
35615153	Recurrent moderate major depressive disorder co-occurrent with anxiety
35615152	Recurrent severe major depressive disorder co-occurrent with anxiety
37109052	Mild major depressive disorder co-occurrent with anxiety single episode
37109053	Moderate major depressive disorder co-occurrent with anxiety single episode
37109054	Severe major depressive disorder co-occurrent with anxiety single episode

	D2.2.3 –Study Protocol for P2 C1-008	
	Author(s): [name], [name]	Version: v3.1 – Final
	Dissemination level: public	

